4.5 Predetermined Covariates and Prognostic Factors

The primary, secondary and exploratory analyses will be based on a mixed model repeated measures (MMRM) ANCOVA, where the covariate in the analysis is the baseline value of the respective response variable. For example, if the number of hours per day spent in the OFF state is being analyzed, the covariate will be the baseline number of hours per day spent in the OFF state. More details are provided in **Sections 9.6.1** to **9.6.3** of this SAP.

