5.8 Change from Baseline

Change from baseline will be the calculated as the later data value minus baseline.

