9 STATISTICAL METHODS

The software used for all summary statistics and statistical analyses will be SAS® (SAS Institute, Inc.)¹ Version 9.2 or later.

Most continuous data will be summarized with the following descriptive statistics unless otherwise noted: number of observations, mean, SD, median, minimum, and maximum; interquartile ranges will be provided as appropriate. Categorical data will be summarized with frequencies and percentages.

Missing data will not be imputed unless otherwise documented in this SAP.

Unless stated otherwise, statistical tests conducted will be two-sided at an α level of 0.05. No adjustment for multiplicity will be made unless otherwise stated in the following sections.

For presentation of data, the mean and median will be presented to 1 decimal place greater than the original data, SD will be to 2 decimal places greater than the original data, and the minimum and maximum will have the same number of decimal places as the original data. P-values, if any, will be reported to three decimal places; p-values less than 0.001 will be reported as p<0.001. The format for minimum and maximum will be "Min, Max". Standard deviation will be abbreviated as "SD".

If a subject is incorrectly dosed, the tables, figures and listings based on the ITT or mITT analysis sets will include a footnote indicating the dosing error.

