9.6.1 Primary Variable

The primary variable, change from baseline to Week 24 in the 3-day average of total awake time in hours per day spent in the OFF state, will be summarized and analyzed in the mITT and repeated in the PPS.

Descriptive statistics (n, mean, standard deviation, median, minimum, and maximum) will be used to summarize results for OFF time by treatment group and week. Only valid diaries (see **Section 5.3**) post baseline are included in the analyses.

At Week 24, a plot of the cumulative distribution (cumulative of subjects) of average change from baseline in OFF state in hours will be displayed.

The null and alternative hypotheses are as follows:

 H_0 : $\mu_a - \mu_p = 0$

 H_1 : $\mu_a - \mu_p \neq 0$

where μ_a and μ_p are the mean changes from baseline to Week 24 in the 3-day average of total awake time in hours per day spent in the OFF state for the tozadenant and placebo groups, respectively.

The primary analysis will be performed on the change from baseline OFF hours using a mixed model repeated measures ANCOVA that includes fixed terms for country/region, treatment group, week (categorical: 2, 6 12, 18 and 24), interaction between treatment group and week, baseline number of hours of OFF time (covariate) and random effect for subject. This model will allow for estimation of treatment effects (each dose regimen of tozadenant vs placebo) separately at each week as well as averaged across weeks.

Restricted Maximum Likelihood (ReML) estimation will be used with an unstructured covariance structure to model the within-patient error and the Kenward-Roger approximation to estimate the

degrees of freedom. If the model does not converge using the unstructured covariance structure, the AR(1) structure may be considered.

MMRM model assumptions including constant variance, normality of errors and normality of random intercepts will be assessed by residual plots.

CONFIDENTIAL

A test of the null hypothesis of the equality of the adjusted group means in the tozadenant and placebo groups will be performed for each dose regimen of tozadenant using a significance level of 5% (two tailed). Treatment differences will be summarized by least squares means (standard errors) and corresponding 95% confidence intervals.

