9.7.3 Laboratory Data

Clinical laboratory values will be evaluated by subject for each laboratory parameter. Laboratory test results will be reported and they will be assigned a LNH classification by each laboratory according to whether the value was below (L), within (N), or above (H) the laboratory reference range. Reference (normal) ranges for laboratory parameters provided by each of the central labs will be included in the clinical study report for this study and will be used for shift tables. Summary tabulations of the continuous clinical laboratory (hematology, chemistry, thyroid function (TSH, free T3 and free T4), and urinalysis) data (n, mean, standard deviation, median, minimum, and maximum) for baseline, each scheduled visit (defined in Table 1), and change from baseline for laboratory data will be provided for the safety analysis set by treatment group. The baseline measurement will be defined as the last assessment prior to the first dose of study drug, including any repeated or unscheduled evaluations. Quantitative urinalysis data will only be listed.

An ANOVA will be performed on change from baseline of last on treatment observation for all continuous clinical laboratory tests, with treatment group as a class variable and within the ANOVA, each tozadenant treatment group will be compared to placebo through estimate statements. The treatment difference from placebo and corresponding p-value will be reported.

Shift from baseline to each scheduled visit will be summarized for the safety analysis set by treatment group for hematology, chemistry, thyroid, and urinalysis variables that are assigned a LNH classification. In addition, shift from baseline to worst post-baseline for the same laboratory variables will be presented based on the LNH classification.

The continuous laboratory hematology, thyroid function (TSH, free T3 and free T4), and urinalysis will have the worst post-baseline value plotted versus the baseline visit for the safety analysis set. The minimum lower limit of normal range and maximum upper limit of normal range amongst laboratories will be drawn in on the x and y axis as vertical lines. The reference normal range will be determined from the normal ranges of all the central laboratories.

All laboratory data will be included in the data listings.

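### The laboratory ANOVA has treatment group as its only term; adding the baseline value as a covariate would tighten the contrasts at almost no cost

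*SAP*

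**What the plan says.** SAP 9.7.3 sets out the between-arm laboratory comparison: "An ANOVA will be performed on change from baseline of last on treatment observation for all continuous clinical laboratory tests". The model has a single factor, the randomized arm, and contrasts set each dose against placebo. The output is specified as "The treatment difference from placebo and corresponding p-value will be reported". No further model term is named.

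The baseline value is defined in the same section: "The baseline measurement will be defined as the last assessment prior to the first dose of study drug, including any repeated or unscheduled evaluations". SAP 5.8 fixes how it enters: "Change from baseline will be the calculated as the later data value minus baseline".

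For the primary, secondary and exploratory analyses, SAP 4.5 specifies a repeated measures ANCOVA "where the covariate in the analysis is the baseline value of the respective response variable". SAP 9.6.1, 9.6.3 and 9.6.4 apply this to OFF time and to the key and other secondary variables. Section 4.5 does not mention safety data.

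The default test level is in SAP Section 9: "Unless stated otherwise, statistical tests conducted will be two-sided at an α level of 0.05". Multiplicity is not adjusted unless stated, and nothing is stated for laboratory tests. The rest of SAP 9.7.3 is descriptive: summaries by visit, low/normal/high shift tables by visit and to the worst post-baseline value, and plots of worst value against baseline for hematology, thyroid and urinalysis. Protocol 11.5.1 plans only descriptive summaries of laboratory data.

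**The concern.** A change score uses the baseline with its slope fixed at 1. A covariate lets the data estimate that slope. When the true slope differs from 1, the change-score contrast carries avoidable noise, and any chance difference between arms at baseline feeds into the estimate.

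The SAP uses the covariate in its efficacy models and gives no reason for leaving it out here. Every patient in the ANOVA must have a baseline value, because the change cannot be formed without one, so the covariate would lose nobody.

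These ANOVAs are the only between-arm tests of laboratory data in either document. The parameters include neutrophils, liver enzymes and thyroid function. Chemistry is not among the worst-versus-baseline plots, so for liver enzymes the ANOVA carries relatively more of the between-arm comparison. At stake is how tightly a mean shift against placebo is estimated.

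**Working it through.** **Inputs from the documents.** Three arms, 1:1:1, 150 per arm (SAP 3.2, 3.3); outcome and model from SAP 9.7.3; change as later value minus baseline (SAP 5.8); two-sided 0.05 (SAP Section 9).

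**Inputs not in the documents.** The correlation r between baseline and last on-treatment value, and the laboratory SDs at the two times. Both are assumed below and shown over a range.

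**The plan's own figure.** The SAP gives no SD, effect or power for any laboratory test. Its nearest stated figure is the primary-endpoint power, which reproduces: 0.9 / (2.6 × √(2/150)) = 0.9 / 0.3002 = 2.998; 2.998 − 1.960 = 1.038; power = 85.0% (84.8% by noncentral t), against 85% stated. This confirms the arm size but does not bear on the laboratory tests.

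**Variance of the two contrasts.** Let s be the common SD at baseline and follow-up.
- Change score, treatment only: residual variance 2s²(1 − r).
- Baseline covariate added: residual variance s²(1 − r²).
- Ratio: (1 − r²) / [2(1 − r)] = (1 + r)/2, which is below 1 for any r below 1.

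The standard error ratio is the square root. The n column is 150 divided by the variance ratio: the arm size at which the planned ANOVA would match the ANCOVA. The last column takes a contrast with 80% power as planned (1.960 + 0.842 = 2.802) and evaluates Φ(2.802/√ratio − 1.960).

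| Assumed r | Variance ratio | SE ratio | Fall in SE | Matching n per arm | Power, if 80% as planned |
|---|---|---|---|---|---|
| 0.5 | 0.75 | 0.866 | 13% | 200 | 89.9% |
| 0.7 | 0.85 | 0.922 | 8% | 176 | 86.0% |
| 0.8 | 0.90 | 0.949 | 5% | 167 | 84.0% |
| 0.9 | 0.95 | 0.975 | 2.5% | 158 | 82.0% |

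A simulation with three arms of 150 and 4,000 runs gave variance ratios of 0.748, 0.860 and 0.954 at r = 0.5, 0.7 and 0.9 (formula: 0.75, 0.85, 0.95). Both estimators were centred on the true difference of zero.

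**Unequal SDs.** With k = follow-up SD / baseline SD, the ratio is k²(1 − r²) / (1 + k² − 2rk). For k of 0.8, 1 and 1.25 crossed with r of 0.5, 0.7 and 0.9, it runs from 0.57 (k = 0.8, r = 0.5: 0.48/0.84) to 0.98 (k = 1.25, r = 0.7: 0.797/0.8125). It equals 1 when rk = 1, for example k = 1.25 and r = 0.8: 0.5625/0.5625. In large samples the covariate does not increase the variance, but there are settings where it gains nothing.

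**Chance imbalance.** With equal SDs, if an arm's baseline mean happens to exceed placebo's by D, the change-score contrast shifts by −(1 − r)D. The ANCOVA contrast removes this shift.

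**The case against.** The case for leaving the plan alone has real weight.

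- **Baseline is already used.** It is subtracted. A reader might infer that the comparison ignores baseline; SAP 5.8 and 9.7.3 show otherwise. Only the estimated slope is missing.
- **There is no bias.** A reader might infer that regression to the mean distorts the comparison. Under 1:1:1 randomization it acts equally in all arms in expectation and cancels in the contrast with placebo. What remains is efficiency and chance imbalance.
- **The SAP breaks no rule of its own.** Section 4.5 confines the covariate to efficacy. It would also be wrong to infer that every efficacy endpoint is baseline-adjusted: CGI-I and PGI-I are first collected at Week 2 and have no baseline, and SAP 9.6.5 makes the exploratory variables descriptive.
- **Signals are mainly sought elsewhere.** There are shift tables, worst-value displays, adverse event recording of clinically significant values (Protocol 11.5.1), liver and neutrophil stopping rules (Protocol 4.3.2), extra hematology draws (Protocol Table 1.1) and a DSMB (Protocol 11.9). A covariate in a model of mean change does nothing for individual outliers.
- **Precision is not the main limit.** Protocol Table 4 lists about 33 continuous blood analytes. With two contrasts each, that is about 66 unadjusted tests, and 66 × 0.05 = 3.3 nominal positives are expected by chance. The trial is not powered on these tests.

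All of this stands as a limit on importance. None of it gives a reason to prefer the treatment-only model, since the covariate uses data already in hand and does not raise the large-sample variance.

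**Conclusion.** The point holds as a minor improvement in efficiency. The planned laboratory contrast is valid under randomization, but it is generally less precise than an ANCOVA on the same data and is exposed to chance baseline imbalance. The fall in standard error is about 13% at r = 0.5 and about 2.5% at r = 0.9. These figures assume equal SDs at the two times and values of r that the documents do not supply, so the size for any given analyte cannot be fixed; where rk is close to 1 the gain vanishes.

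A reader might go further and conclude that real laboratory harm is likely to be missed. The documents do not support that: the shift tables, worst-value displays and individual stopping rules are untouched by the choice of model. The primary and key secondary analyses and the sample size are also unaffected.

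**What to change.** In SAP 9.7.3, replace the ANOVA sentence with: *An ANCOVA on change from baseline to the last on-treatment observation, with treatment group and the baseline value of the parameter as terms.* The contrasts of each dose with placebo stay as they are.

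The cost is one model term, with no new data and no patient lost. SAP Section 8 declares only the primary and secondary efficacy analyses final, so it does not bar this edit. SAP Section 1 says the plan was written against protocol Amendment No. 1, while the protocol supplied is Amendment No. 3; the change could be made in any update that aligns the two.

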9.7.4 Systolic and Diastolic Blood Pressure and Pulse Rate

Systolic and diastolic blood pressure and pulse rate will be measured in both the supine and standing positions. The scheduled visits that will be summarized are Weeks 2, 6, 12, 18, 24 and early termination. In addition, on Day 1, there are to be 3 measurements for both supine and standing, respectively, at least 10 minutes apart. Orthostatic change (difference between standing and supine) in systolic and diastolic blood pressure and pulse rate will be derived. The baseline value for the supine and standing blood pressure and pulse rate will be the average of the 3 measurements taken at least 10 minutes apart prior to first dose on Day 1, as defined in **Section 5**.

Summary tabulations of the systolic and diastolic blood pressure and pulse rate in both standing and supine positions as well as the orthostatic change (n, mean, standard deviation, median, minimum, and maximum) for baseline, each scheduled visit, and change from baseline will be

provided for the safety analysis set by treatment group. In addition, the placebo corrected mean change from baseline (tozadenant treatment group mean change from baseline minus placebo mean change from baseline) for systolic and diastolic blood pressure and pulse rate in both standing and supine positions as well as the orthostatic change will be summarized (n, mean, standard deviation, median, minimum, and maximum) for the safety analysis set by treatment group.

CONFIDENTIAL

At each scheduled post-baseline visit and time point (Weeks 2, 6, 12, 18, 24 and early termination), the number and percent of subjects meeting each abnormal criteria displayed below will be summarized by treatment group.

- Supine and standing systolic blood pressure
 - ≥160 mmHg
 - < 100 mmHg

 - ≥20 mmHg increase from baseline
 - ≥20 mmHg decrease from baseline
 - ≥40 mmHg increase from baseline
 - ≥40 mmHg decrease from baseline
- Supine and standing diastolic blood pressure
 - ≥100 mmHg
 - <50 mmHg
 - ≥10 mmHg increase from baseline
 - ≥10 mmHg decrease from baseline
 - ≥20 mmHg increase from baseline
 - ≥20 mmHg decrease from baseline
- Supine and Standing Pulse rate
 - ≥120 bpm
 - <48 bpm
 - ≥30 bpm increase from baseline
 - ≥30 bpm decrease from baseline
- Orthostatic change ≥20 mmHg increase from baseline for systolic blood pressure and diastolic blood pressure
- Orthostatic change ≥20 mmHg decrease from baseline for systolic blood pressure and diastolic blood pressure

For Weeks 2, 6, 12, 18 and 24, plots of the mean change from baseline and placebo corrected mean change from baseline at each timepoint will be displayed for blood pressure and pulse rate in supine and standing position and orthostatic change for the safety analysis set.

All vital sign data collected on the eCRF will be included in the data listings.

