4.3.2 Definite Criteria for Withdrawal from Study

Patients must be discontinued from the study if any of the following events occur:

- 1. Patient develops an illness that would interfere with his or her continued participation.
- 2. Patient withdraws his or her consent.
- 3. Confirmation of patient pregnancy during the study, as evidenced by a positive pregnancy test.
- 4. The Sponsor's designee or a regulatory agency requests withdrawal of the patient.
- 5. The Sponsor or a regulatory agency terminates the study.
- 6. Patient has active suicidality since last visit as indicated by a positive response ("Yes") to either Question 4 or Question 5 of the C-SSRS, or reports any suicidal behavior since their last C-SSRS assessment. The patient should be referred immediately to a Mental Healthcare Professional.
- 7. The patient has a QTcF interval consistently ≥ 500 msec and/or a QTcF interval consistently increased by ≥ 60 msec compared to the average baseline QTcF interval. The average baseline QTcF interval is defined as the average of the three QTcF interval values obtained at Visit 2. Fridericia's method must be used for correction of QT intervals.
- 8. Investigators must follow guidelines provided related to monitoring hepatic parameters in relation to investigation guidelines and stopping rules. The following necessitate immediate cessation of dosing with IMP:

- a. Patients with alanine transaminase (ALT) or aspartate transaminase (AST) >8x ULN.
- b. Patients with ALT or AST $\ge 3x$ ULN and co-existing total bilirubin $\ge 2x$ ULN*.
- c. Patients with ALT or AST $\ge 3x$ ULN who exhibit a temporally associated fatigue, nausea, vomiting, right upper quadrant pain or tenderness, fever (without clear alternative cause), rash or eosinophilia (>5%).
- *Patients with significant elevation of ALP (ALP >2x ULN) indicating biliary obstruction to be discussed with the Medical Monitor.
- 9. Patients noted to have an elevated BP post-baseline, with a systolic BP \geq 160 mmHg and/or a diastolic BP \geq 100 mmHg that is present at 2 consecutive post-baseline study visits.

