11.5 Planned Safety and Other Analyses

11.5.1 Safety Analyses

The primary safety variables will be the occurrence of TEAEs including nonserious and serious TEAEs, and TEAEs leading to permanent withdrawal of study medication during the study.

All AEs will be presented by Medical Dictionary for Regulatory Activities (MedDRA) system organ class, high level term and preferred term. The data will be displayed as number of patients experiencing the AEs, percentage of patients and number of AEs.

Safety data, including AEs, vital signs, ECGs, ESS including assessment of episodes of sudden onset of sleep, C-SSRS, mMIDI, physical and neurological examination, clinical laboratory test results, and concomitant medications will be summarized descriptively for each treatment group and for the entire tozadenant group, where appropriate. The descriptive statistics will be provided for the observed data and for the change from Baseline at each measured time point. Tables will summarize AE data as appropriate by dose group. Note that counting will be by patient, not event and patients are only counted once within each MedDRA system organ class (SOC) or preferred term (PT).

Clinical laboratory tests results, vital signs, ECGs, dyskinesia as measured by questions 32, 33 and 34 of UPDRS Part IV, ESS, weight, physical and neurological examination results, and UPDRS will be summarized descriptively. Descriptive statistics will be presented for continuous variables utilizing the observed data and the change from baseline (at each measured time point). Frequencies and percentages will be presented for categorical variables. Laboratory test results will be classified as below the lower limit of normal, within normal limits and above the ULN. Shift tables will be used to summarize changes from Baseline to each visit by treatment group. Clinically significant physical or neurological examination findings and any clinically significant out-of-range laboratory tests are recorded as adverse events and will be documented in the AE summaries.

Analyses will be performed for the SS as randomized.

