15.6 Assessment for Episodes of Sudden Onset of Sleep

Assessment for Episodes of Sudden Onset of Sleep

Definition of sudden onset of sleep: Abrupt episodes of unplanned sleep during activities of daily living where they are not expected to occur. These events may or may not be preceded by somnolence or sedation.

Instruc	ctions for the Baseline Visit:				
Did the subject experience any sudden onset of sleep in the last 6 weeks? (Check only 1 box)					
	Yes, but the subject felt sleepy before (This is an indication of a possible sudden onset of sleep).				
	Yes, subject fell asleep completely unexpected without prior sleepiness (This is an indication of a possible sudden onset of sleep).				
	Yes, sometimes with, sometimes without prior sleepiness (This is an indication of a possible sudden onset of sleep).				
	No				
	bject responds "Yes" to any of the above, the investigator should record the applicable response into the substitute Medical History. (e.g., "possible sudden onset of sleep")				
Instruc	ctions for Visits After Baseline:				
	ctions for Visits After Baseline : e subject experience any sudden onset of sleep since the last visit? (Check only 1 box)				
	e subject experience any sudden onset of sleep since the last visit? (Check only 1 box)				
	e subject experience any sudden onset of sleep since the last visit? (Check only 1 box) Yes, but the subject felt sleepy before (This is an indication of a possible sudden onset of sleep). Yes, subject fell asleep completely unexpected without prior sleepiness (This is an indication of a possible				
	e subject experience any sudden onset of sleep since the last visit? (Check only 1 box) Yes, but the subject felt sleepy before (This is an indication of a possible sudden onset of sleep). Yes, subject fell asleep completely unexpected without prior sleepiness (This is an indication of a possible sudden onset of sleep). Yes, sometimes with, sometimes without prior sleepiness (This is an indication of a possible sudden onset				

study.

subject's continued participation in the study puts them at risk and whether they should be discontinued from the

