9.7.6 Columbia-Suicide Severity Rating Scale

The C-SSRS is a semi-structured interview that captures the occurrence, severity, and frequency of suicide-related thoughts and behaviors during the assessment period. The interview includes definitions and suggested questions to solicit the type of information needed to determine if a suicide-related thought or behavior occurred.

The interview measures presence of suicidality, specifically suicidal ideation (including intensity of ideation) and suicidal behavior.

The C-SSRS must be performed by an individual who is trained in its use and certified to perform the assessment.

Two versions of the C-SSRS are used in this study: the "Baseline/Screening" version, and the "Since Last Visit" version.

The C-SSRS "Baseline" version is completed at Screening (Visit 1), and C-SSRS "Since Last Visit" version is completed at all subsequent visits.

All C-SSRS data collected on the eCRF will be included in the data listings. The number and percent of subjects reporting "Yes" for each of the 5 questions to suicidal ideation and 6 questions about suicidal behavior will be summarized by treatment group and visit. In addition, for suicidal behavior, the total number of actual attempts, total number of interrupted attempts and total number of aborted attempts will be summarized (n, mean, standard deviation, median, minimum and maximum) by treatment group and visit.

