9.7.8 Episodes of Sudden Onset of Sleep

The sudden onset of sleep will be recorded at baseline and Weeks 0, 2, 6, 12, 18 and 24 as well as Early Termination. The responses to "did the subject experience any sudden onset of sleep" will be summarized by count and percentages by treatment group and visit. Shift from baseline to each scheduled visit will be summarized for the safety analysis set by treatment group for each sudden onset of sleep questions. All data collected on the episodes of sudden onset of sleep will be included in the data listings.

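### Blood-pressure and pulse outliers, C-SSRS answers and sudden sleep are summarized by visit only, so the SAP never counts the patients who ever met a limit or who met the protocol's two-visit blood-pressure event

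*SAP*

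**What the plan says.** **Blood pressure and pulse (SAP 9.7.4).** The outlier table is specified as "At each scheduled post-baseline visit and time point (Weeks 2, 6, 12, 18, 24 and early termination), the number and percent of subjects meeting" the abnormal limits, counted one by one. These include 160 mmHg systolic and 100 mmHg diastolic, supine and standing. Early termination is a separate row. No row covers any post-baseline visit, and the percentage denominator is not defined.

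**C-SSRS (SAP 9.7.6).** Answers to the five ideation and "6 questions about suicidal behavior will be summarized by treatment group and visit".

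**Sudden onset of sleep (SAP 9.7.8).** Responses "will be summarized by count and percentages by treatment group and visit". The only other summary is a shift table: "Shift from baseline to each scheduled visit will be summarized for the safety analysis set by treatment group".

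**Protocol 11.5.1** adds no patient-level count for these measures: "The descriptive statistics will be provided for the observed data and for the change from Baseline at each measured time point".

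**Withdrawal (protocol 4.3.2).** The list is mandatory: "Patients must be discontinued from the study if any of the following events occur". It includes systolic pressure of at least 160 and/or diastolic of at least 100 mmHg that is "present at 2 consecutive post-baseline study visits". It also includes a Yes to C-SSRS Question 4 or 5, or any suicidal behavior.

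**Contrast within the SAP.** Section 9.7.3 plans a shift from baseline to the worst post-baseline laboratory value. Section 9.7.10 classifies each patient by maximum post-dose QT, QTcB and QTcF.

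**The concern.** The outlier table uses the same 160/100 limits as the withdrawal rule but never counts the event that the rule defines. Patients with persistent high readings leave after their second one, so later rows describe those who remain. If tozadenant raised blood pressure in some patients, its later rows could move toward placebo because those patients had gone.

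Even without removal, visit percentages cannot be added up to patients. The same 5% at each visit can be the same patients throughout or different patients each time. For sudden sleep and suicidality this bears on the stated objective, since protocol 2.1.4 and SAP 2.4 ask about their occurrence. For blood pressure the objective is worded more loosely, as an evaluation based on vital signs.

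**Working it through.** **Inputs from the documents.** There are 150 patients per arm (SAP 3.2) and five scheduled post-baseline visits: Weeks 2, 6, 12, 18 and 24. The plan's own figure reproduces: 0.9 / (2.6 × √(2/150)) = 3.00, and Φ(3.00 − 1.96) = 0.85, the stated 85% power (0.848 by the noncentral t). It fixes the denominator only. The documents give no expected rate for any of these safety measures, so **every event rate below is an assumption**.

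**1. Blood pressure, risk concentrated in some patients.** A fraction f is prone, with probability 0.8 of a high reading per visit; the rest have 0.02. Patients leave after two consecutive high readings, and there is no other dropout.

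- First-visit rate = 0.8f + 0.02(1 − f). This is 5.9% for f = 5% and 9.8% for f = 10%.
- Risk at any of five visits = 1 − [f × 0.2⁵ + (1 − f) × 0.98⁵]. This is 14.1% (about 21 of 150) and 18.6% (28 of 150).
- Week 12 row for f = 10%: removed after Week 6 = 0.10 × 0.64 + 0.90 × 0.0004 = 0.0644. Those remaining with a high reading = 0.036 × 0.8 + 0.8996 × 0.02 = 0.0468. The row is 0.0468 / 0.9356 = 5.0%.

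| Assumed prone fraction | Wk 2 | Wk 6 | Wk 12 | Wk 18 | Wk 24 | Wk 24 without removal | Any visit |
|---|---|---|---|---|---|---|---|
| 5% | 5.9% | 5.9% | 3.5% | 2.9% | 2.4% | 5.9% | 14.1% |
| 10% | 9.8% | 9.8% | 5.0% | 4.0% | 2.9% | 9.8% | 18.6% |

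**2. Blood pressure, the same random 5% in everyone.** The rows stay flat at 5.0%. Any visit: 1 − 0.95⁵ = 22.6% (34 of 150). Two consecutive visits, by full enumeration: 0.96%.

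**3. Blood pressure, staggered onset.** Four new patients of 150 become persistently high at each visit and leave after their second high reading. The rows are 4/150, 8/150, 8/146, 8/142 and 8/138, that is 2.7, 5.3, 5.5, 5.6 and 5.8%. Yet 20/150 (13.3%) ever met the limit and 16/150 (10.7%) met the two-visit event. Without removal, Week 24 would read 20/150 = 13.3%.

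From Week 6 on, the rows in cases 2 and 3 are close (5.0% against 5.3 to 5.8%), while the two-visit event differs about elevenfold (0.96% against 10.7%). The early-termination row would give a hint, since 150 − 138 = 12 patients in case 3 leave before Week 24, but it is not a cumulative count.

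**4. Sudden sleep, no automatic removal.** A row of 1 to 5% at each visit fits a patient-level risk of 1 to 5% (same patients each time) up to 1 − 0.99⁵ = 4.9% to 1 − 0.95⁵ = 22.6% (independent).

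**5. C-SSRS.** A constant 1% per interval gives 1 − 0.99⁵ = 4.9% of patients. For Questions 4 and 5 and behavior, the first Yes triggers withdrawal, so summing one item's visit counts comes close to a patient count. Ideation Questions 1 to 3 trigger nothing and can recur in the same patient, and one patient can be positive on several items.

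**The case against.** The plan is not blind to these patients.

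- **Adverse events and disposition.** SAP 9.7.1 and 9.7.2 count adverse events by subject within each term. SAP 9.1 tabulates withdrawals with reasons by arm. A reader might therefore infer from the by-visit tables that no patient-level risk is reported at all; the documents do not support that. What stands is that these tables see a high reading or a Yes only if it was recorded as an adverse event or a withdrawal reason. Protocol 11.5.1 says that clinically significant examination findings and laboratory values are recorded as adverse events; it does not name blood-pressure readings or C-SSRS answers there. Patients who met a limit once and stayed are missed.
- **Early termination.** Withdrawn patients are asked to attend a visit with blood pressure and C-SSRS (protocol 6.2.32), and SAP 9.7.4 gives that visit its own row. They do not vanish. Nor does the SAP say that they leave the denominator, since it defines none.
- **Telling patterns apart.** It is tempting to say that the table cannot separate persistent from chance readings. That goes too far. If 15 of 150 are high at Weeks 2 and 6 and then leave, the rows are about 10, 10, 0, 0, 0%, plainly different from a flat 5%, and the first two rows show the cumulative risk exactly.
- **Cleaner later visits.** This is not general. With uniform random risk the rows stay flat. A single high reading does not remove anyone, and for sudden sleep discontinuation is case by case (protocol 9.5.5).
- **Recall window.** The Baseline item asks "Did the subject experience any sudden onset of sleep in the last 6 weeks", while later visits ask since the last visit: 2 weeks at Week 2, 4 weeks at Week 6 and 6 weeks thereafter. A reader might infer a biased arm comparison. The mismatch affects only Weeks 2 and 6 and is the same in every arm, so it does not.
- **Proportion.** SAP 9.7.4 has 12 systolic, 12 diastolic and 8 pulse limits. A confidence interval for each of 32 limits at two doses would mean 64 intervals in a mainly descriptive safety plan. That part of the objection stands and limits the fix.
- **Deferred shells and listings.** Table shells come later and all data are listed. Listings do not replace a prespecified count.

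**Conclusion.** The gap is real but narrow. These three sections prespecify neither a count of patients meeting a criterion at any post-baseline assessment nor a count of the two-visit blood-pressure event, although the SAP has a worst or maximum summary for laboratory tests and QTc. In the assumed blood-pressure examples of cases 1 and 2, the any-visit risk is 1.9 to 4.5 times the highest visit percentage (18.6/9.8 and 22.6/5.0). Removal lowers the Week 24 row from 5.9% to 2.4%, or from 9.8% to 2.9%, but only where risk is concentrated in some patients.

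The sizes rest on assumed rates, five visits and no other dropout. The SAP was written on Amendment 1 and the protocol supplied is Amendment 3; the documents do not show whether the blood-pressure rule was already in Amendment 1. The point does not depend on that: the rule is in the current protocol and the SAP does not count it. This is a cheap improvement to the safety tables and does not affect the efficacy analysis.

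**What to change.** Add to SAP 9.7.4, 9.7.6 and 9.7.8, by arm and with all Safety Set patients as denominator, the number and percent of patients:

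- (a) meeting each SAP 9.7.4 blood-pressure or pulse limit at any post-baseline Part A assessment, including unscheduled and Early Termination visits. Protocol 6.2.34.2 allows blood pressure at unscheduled visits, which the planned outlier table omits;
- (b) at or above 160 and/or 100 mmHg at two consecutive post-baseline visits. Protocol 4.3.2 does not say supine or standing, so state the position consistently with how that rule is applied;
- (c) with any post-baseline C-SSRS ideation or behavior, and with any post-baseline sudden-sleep episode. Compare the sudden-sleep row between arms, not with the 6-week Baseline recall.

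A tozadenant minus placebo risk difference with 95% CI may be limited to (b) and (c). State the denominator of the by-visit percentages and keep those tables.

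The cost is SAP wording and a few descriptive rows from data already collected. No visit, assessment or clinical rule changes.
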